4. STUDY POPULATION

4.1. List the number and nature of subjects to be enrolled.

45 adolescents, aged 10-17 years old, will be recruited in KKH

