The investigator will determine the eligibility of the patients. If the patient is found to be eligible and willing to participate, written consent to participate in the trial will be taken by the nurse coordinator or the clinical research coordinator. The patient's weight and height, body fat composition, waist circumference and blood pressure will be measured as per usual standard protocol or by the study team members and Co-I. Questionnaires to assess eating, quality of life and dietary recall will be administered as part of the research. Accelerometers are optional for patients and will be fitted to assess physical activity. The purpose and instructions for use of activity monitor will be explained, with a copy of the guidelines / instructions provided to all participants. During the measurement period, they will be required to complete an activity diary, providing information on activities / exercises engaged in during the measurement period. In the event the device is removed, they will be required to provide details (e.g, reason and duration) in the activity diary. As the participants will be required to wear the activity monitor throughout the day, including during school activities, a letter to the school / teacher will be provided to explain the reason for wearing the device during the study period. Participants will need to complete a 3-day food diary.

Visit 1 (preferably before visit 2):

Metabolic blood tests (HbA1C, fasting lipid panel, oral glucose tolerance test, fasting insulin level and liver function test) were collected after a minimum 8 hour fasting period together with bloods for AAA, BCAA, long chain acylcarnitines and **vitamin D level, calcium, magnesium, phosphate and alkaline phosphatase** and are optional for participants. Participants may choose to return the accelerometer and food diary during this visit.

Telephone call (before visit 2):

Phone call reminders of the upcoming visit will be provided by the study team member.

Visit 2 (preferably between 4-11 weeks):

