8. SAMPLE SIZE AND STATISTICAL METHODS

8.1. Determination of Sample Size

There is no sample size calculation for this pilot study. The Weight Management Clinic receives new referral to WMC of 20 new patients per month with approximately 20% of the new referrals being adolescents (10). Using a conservative estimate of 50% uptake rate, we will be able to get 2 patients per month over 20 months to get 45 adolescents enrolled into Kurbo program.

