8.2. Statistical and Analytical Plans

Data will be analysed using SAS version 9.3 for Windows (SAS, Inc., Cary, NC USA). BMI will be calculated as kg/m² and BMI-z score calculated using the L, M, S parameters published by the CDC. (34) Baseline demographic, anthropometric measurements, parental BMI, quality of life measurement, disordered eating and physical activity were compared between those in low risk WMC versus those in high risk WMC using the Wilcoxon rank-sum test and the two-sample-t-test for non-normal and normal continuous variables, respectively, and the Fisher's exact test for categorical variables. Changes in cardiometabolic risk factors between first visit and at month 12 will be compared using the paired-sample t-test. Generalized linear mixed model will be carried out on the BMI z-score over multiple visits over 12 month follow up period. The mean value of BMI z-score is considered as a function of time from the baseline. The variance components is used as the covariance structure in generalized linear mixed model. It models a different variance component for each random intercept to allow each child to have his/her own overall level of BMI z-score after taking into account baseline covariate. A time-group interaction will be included to test whether the rate of change of BMI z-score is different between adolescents in low risk and high risk WMC.

There is no reason to assume that this project will lead to an excess of adverse events as the waitlist intervention consists of advice from the nurse and offer of referral to a Kurbo program, neither of which seem likely to create harm. Nonetheless, there are several safety net in place for the waitlist intervention. Firstly, as part of standard Kurbo procedures, any excessive weight loss or weight gain will prompt the Kurbo coaches to inform parents to seek help from their GP and the WMC nurse coordinator will be informed if any concerns arise. Secondly, the WMC nurse coordinator will have administrative rights to Kurbo program and will be able to monitor patient's weight data and communication with Kurbo coaches and will highlight any concerns that arise as a result of intervention. There will also be a feedback form (A month 3 evaluation) administered by the clinical research coordinator on the participants' attitudes to the waitlist intervention and to identify any adverse events at the first WMC visit. As this is a pilot study, there will be no interim analyses.

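### Section 8.2 gives the BMI z-score model only a random intercept, so its slope test can be anti-conservative if children within a risk group differ in rate of change

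*Combined protocol and SAP*

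**What the plan says.** Section 8.2 plans a generalized linear mixed model for repeated BMI z-scores, with the mean a function of time from baseline. On the covariance it says: "The variance components is used as the covariance structure in generalized linear mixed model". On the random effects it says: "It models a different variance component for each random intercept to allow each child to have his/her own overall level of BMI z-score". The hypothesis test follows: "A time-group interaction will be included to test whether the rate of change of BMI z-score is different" between the two clinics.

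Nothing in Section 8.2 mentions a child-specific slope, serial correlation of residuals, a sandwich standard error, a degrees-of-freedom method or a significance level. Section 8.1 states: "There is no sample size calculation for this pilot study". Section 4.1 sets the number of children at 45. Table 1 in Section 5 marks anthropometry at four times: baseline and Visits 2, 3 and 5.

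**The concern.** The model lets children differ in level but makes all children in a clinic group share one slope, and slope is what the interaction tests. If children in the same group truly change at different rates, a child's visits are correlated in a way that the model ignores. Four visits from one child are then counted as more information about the group's slope than they carry. The standard error comes out too small, the confidence interval too narrow, and chance differences are declared significant too often. The same applies to the standard error of mean change over time, which bears on the first secondary objective (BMI z-score change at 3 and 6 months).

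**Working it through.** **The plan's own figures.** The documents give no standard error, power or error rate for this model, so there is none to reproduce. The only size figure is 45 children. The accrual text gives 20 × 20% × 50% = 2 per month, and 2 × 20 months = 40, not 45. That discrepancy does not affect this point, because the result below hardly depends on sample size.

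**Inputs from the documents.** 45 children (Section 4.1). Visit windows of weeks 4–11, 12–23 and 24–36 after baseline (Section 5), with midpoints 7.5, 17.5 and 30 weeks, or about 0, 1.75, 4 and 7 months. Section 8.2 speaks of 12 months of follow-up, whereas the Section 5 schedule ends at week 36; the schedule is used here.

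**Assumed inputs, not in the documents.** Linear time; two-sided alpha of 5%; between-child SD of true slope 0 to 0.30 z per 6 months (about 26 weeks); within-child residual SD 0.05 to 0.15 z.

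**Formula.** Take T common visit times, residual variance s², within-group slope variance t², and Sxx the sum of squared centred times. Let r = t²·Sxx/s².
- True variance of one child's fitted slope: t² + s²/Sxx = (s²/Sxx)(1 + r).
- The random-intercept model absorbs slope variation into its residual, which becomes about s²(1 + r/(T−1)), and so reports (s²/Sxx)(1 + r/(T−1)).
- Ratio of true to reported variance: R = (1 + r)/(1 + r/(T−1)).
- Type I error ≈ 2[1 − Φ(1.96/√R)].

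The factor for number of children cancels, so R applies equally to a mean slope and to a difference in slopes.

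**Worked case.** The mean visit time is 3.1875 months, so Sxx = 10.16 + 2.07 + 0.66 + 14.54 = 27.4. With slope SD 0.20 per 6 months (0.0333 per month) and residual SD 0.10, r = 0.00111 × 27.4/0.01 = 3.05. Then R = 4.05/2.02 = 2.01, the reported SE is 1/√2.01 = 0.71 of the true SE, and type I error is 16.7%.

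**Simulated rejection rate of the random-intercept model.** 45 children, 6,000 runs per cell, no true group difference, groups independent of the outcome. The reported-to-true SE ratio from the formula is in brackets.

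| Slope SD per 6 months | Residual SD 0.05 | Residual SD 0.10 | Residual SD 0.15 |
|---|---|---|---|
| 0 | 4.8% (1.00) | 5.2% (1.00) | 5.1% (1.00) |
| 0.05 | 9.6% (0.84) | 7.0% (0.95) | 5.6% (0.97) |
| 0.10 | 16.0% (0.71) | 11.2% (0.84) | 7.4% (0.91) |
| 0.20 | 23.4% (0.62) | 16.9% (0.71) | 12.0% (0.79) |
| 0.30 | 24.9% (0.60) | 21.4% (0.65) | 17.5% (0.71) |

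As r grows, R tends to T − 1, so the formula has a ceiling: 25.8% with four visits and 16.6% with three.

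**Sensitivity.** At slope SD 0.20 and residual SD 0.10, a 10/35 split gives 17.4% and 25 children give 17.5%. REML fits with visits spread over the windows and 20% of follow-up visits missing (300 runs each, residual SD 0.10) give 6.0%, 10.0% and 17.7% at slope SD 0, 0.10 and 0.20.

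**With child-specific slopes.** In the same balanced simulations, a test on child slopes rejects in 4.5% to 5.8% of trials in every cell, again with groups independent of the outcome.

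**With groups formed from the outcome.** Section 5 places children largely by BMI percentile change up to Visit 2. Simplifying that rule to the sign of the observed baseline-to-Visit-2 change in z-score, with no slope variation, no true difference and residual SD 0.10, the rejection rate is 24.2% with the random intercept and 24.4% with child-specific slopes.

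**The case against.** The strongest reply is that the inflation is conditional. It depends on the ratio of within-group slope variance to residual variance, and the documents give neither. A reader might infer from the missing random slope that the false-positive rate is well above 5%. The documents do not support that as a fact. Only variation within a risk group matters, and triage turns some of the spread between responders and non-responders into the group effect. The school-based pilot in Section 1 (among children who lost weight, 58% cut BMI by more than 3% and 20% by more than 7%) shows one change per child, in a selected subset, and cannot separate true slope from noise. Section 5 also accepts self-reported height and weight after missed visits, which could raise residual SD and shrink the inflation. All of this stands, and it is why the range starts near 5.5%.

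The wording on variance components is also loose enough that further random effects are not excluded. That is a reason to write the model out, since the text as it stands describes differences in level only.

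Finally, this is a pilot whose primary objective is the proportion triaged to the low risk clinic, and the slope comparison is not among the eight listed secondary objectives. That limits the consequences. It does not justify specifying a test whose standard error may be too small.

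**Conclusion.** The concern holds as a conditional one. Section 8.2 specifies only a random intercept for a test on slopes. If true slopes vary within a risk group, the reported standard error is too small: by formula, 0.97 down to 0.60 of its true value over the assumed range. The corresponding rejection rate is roughly 5.5% to 25% at a nominal two-sided 5%, and about 5% if slopes do not vary. The direction is certain once slopes vary; the size rests on assumed SDs and an assumed alpha. The rejection rates were simulated for the interaction only. The effect on the standard error of mean change follows from the formula.

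A reader might also infer that a random slope makes the low- versus high-risk test hold its level. It does not. That result requires group to be independent of the outcome, whereas Section 5 forms the groups largely from BMI change that is also in the model. Under that rule, simplified as above, both models rejected in about 24% of trials. Warranting a change at little cost, this is a weakness in a secondary analysis and does not touch the primary objective.

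**What to change.** In Section 8.2, add a random slope for time with an unstructured 2x2 covariance with the intercept. State the structure explicitly, because a variance-components structure would set the intercept–slope covariance to zero. An alternative is an unstructured covariance over the four anthropometry visits (4 × 5/2 = 10 parameters, with visits treated as fixed slots despite wide windows). Fit by REML with Kenward-Roger degrees of freedom. Pre-specify the fallback on non-convergence: the random intercept with a small-sample-corrected sandwich standard error. State alpha and sidedness.

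The cost is a few lines in the SAP, a small change to the SAS call, wider confidence intervals and some risk of non-convergence with 45 children. If slopes turn out not to vary, little is lost: the child-slope test held 5.0% to 5.5% at zero slope variance.

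Add a sentence saying that this corrects the standard error only, and that the low- versus high-risk slope test should not be described as a 5% test until the outcome-based grouping has been dealt with separately.

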9. DIRECT ACCESS TO SOURCE DATA/DOCUMENTS

The investigator(s)/institution(s) will permit study-related monitoring, audits and/or IRB review and regulatory inspection(s), providing direct access to source data/document.

10. QUALITY CONTROL AND QUALITY ASSURANCE

The study will be conducted in accordance with the current protocol and the Principal Investigator and clinical research coordinator are SG-GCP registered. As this is an unblinded study with no substantial risk, the Principal investigators, together with the Co-Investigators and research coordinators, who are responsible for the day-to-day management of the trial, will ensure that the research methodology is adhered to and that appropriate action is taken to ensure to safeguard participants and the quality of the trial itself. They will also meet at least quarterly throughout the course of the trial. Data entered by the clinical research coordinator will be counter checked by the investigators to ensure that the data correlates with the case report forms.

11. ETHICAL CONSIDERATIONS

This study will be conducted in accordance with the ethical principles that have their origin in the Declaration of Helsinki and that are consistent with the Singapore Good Clinical Practice and the applicable regulatory requirements.

This final study protocol, including the final version of the Participant Information Sheet and Consent Form, must be approved in writing by the Centralised Institutional Review Board (CIRB), prior to enrolment of any patient into the study.

The principle investigator is responsible for informing the CIRB of any amendments to the protocol or other study-related documents, as per local requirement.

11.1. Informed Consent

Physicians, nurses, clinic assistants and wards assistants in the outpatient clinics and the inpatient wards will be informed about the study. When the patient is referred to the weight management clinic, the clinical research coordinator will be informed about the referral. A trial screening form will be completed by the clinical research coordinators to identify potential participants; the research team will ask to keep a copy of this if a person is eligible for the study but declines participation. This is to compare the characteristics of people who participate to those who do not.

Consent process will take place in an outpatient clinic setting after a physician referred the patient to the weight management clinic. The physician or clinic assistant will inform the study team members about potential research participants. Consent process will take place in an outpatient clinic consultation room which is quiet and free of interruptions.

The research coordinator or nurse coordinator will provide the Participant Information Sheet and Consent Form to the participant and parent for reference. If participant and parent are agreeable to the research study then the research coordinator/nurse coordinator will obtain written informed consent to participate in the trial. Participants are also free to consider and contact the research coordinator if they require time to consider their participation. A letter of invitation will be sent to invite eligible participants to participate in the study before the appointment if study team members are unable to recruit the patient at the point of referral. Participants can contact the research coordinator or the nurse clinician if they have any queries regarding the study. The nurse clinician or other co-investigators, who are not directly involved in the care of the participant, will be conducting the consent process to reduce the possibility of coercion or undue influence. Participants are also free to withdraw from the study anytime as documented in the consent form which is provided in the Participant Information Sheet and Consent Form provided to participants. Participants' assent will be obtained together and documented using the full consent form, together with the documented consent form of the parent or legal guardian.

11.2. Confidentiality of Data and Patient Records

Hardcopy of the data will be stored in a cupboard with lock and key access in an access controlled room. Soft copy of the data will be stored in a password protected file. Only study team members and the research coordinators will have access to the research data. Research data will be stored in a password protected file with only team members and research coordinators having access to the password. The records will be accessible for inspection and copying by authorized authorities and will be stored for 7 years after the study is completed.

12. PUBLICATIONS

The Investigators will be involved in reviewing drafts of the manuscripts, abstracts, press releases and any other publications arising from the study. Authorship will be determined in accordance with the ICMJE guidelines and other contributors will be acknowledged. The funding source's contribution will be acknowledged but will have no contribution in publication decisions.

13. RETENTION OF STUDY DOCUMENTS

Records for all participants, including CRFs, all source documentation (containing evidence to study eligibility, history and physical findings, laboratory data, results of consultations, etc.) as well as IRB records and other regulatory documentation will be retained by the PI in a secure storage facility under key and lock. The records will be accessible for inspection and copying by authorized authorities and will be stored for 6 years after the study is completed.

14. FUNDING and INSURANCE

Grant agency is Paediatrics Academic Clinical Programme under the grant name: Tan Cheng Lim Research and Education Fund Grant Award. The grant has been approved with the budget allocation of \$50,000 over 1.6 years from 01 April 2017 to 30 November 2018.

The participants will be reimbursed SGD50 to compensate the travelling expenses for each visit they attend in the window period.

List of Attachments

